### 5.5 Interim Analysis

No interim analysis is planned.

### 5.6 Timing of Final Analyses

There will be 2 database locks for this study:

- A provisional database lock after all patients complete the Day 169 visit to allow for the analysis of safety and efficacy data through Day 169.
- A final database lock after all patients complete the study to allow for the analysis of any safety data collected after Day 169.

For each database lock, applicable EDC data will be locked in order to protect write access after the following preconditions are fulfilled:

- All records are entered in the database.
- All AE are coded to the satisfaction of the Chief Medical Officer.
- All medications are coded to the satisfaction of the Chief Medical Officer.
- All data queries have been resolved.
- All decisions have been made regarding all protocol violations and ITT population exclusions.
- Written authorizations to lock the database are obtained from Allakos Clinical Data Management and the Chief Medical Officer.

The randomization code for this study will not be revealed until the previous preconditions are fulfilled and documentation of the provisional database lock is complete. After the provisional database lock, the randomization code will be made available to a restricted number of individuals at Allakos who are involved in the analysis of data. Data analysis will commence after the provisional data lock and the final database lock, respectively. In addition, the PK and ADA data may be locked and assessed separately.

### 5.7 Multicenter Study

Supplemental analysis will be performed pooling data across study sites.

The study will have approximately 90 sites. Analysis of site effect will be based on analysis centers. Analysis centers will be formed in such a way that there are sufficient subjects per pooled analysis center for the assessment of site effects. Sites from the following geographic clusters have been identified for pooling data across study sites:

- **Analysis Center 1:** Massachusetts, Connecticut, Rhode Island, New York, New Jersey, Pennsylvania, District of Columbia, Maryland, Maine, Vermont, Delaware, and New Hampshire
- **Analysis Center 2:** Virginia, West Virginia, South Carolina, Georgia, Mississippi, Florida, Alabama, Louisiana
- **Analysis Center 3:** North Carolina, Tennessee, Ohio, Michigan, Indiana, Kentucky
- **Analysis Center 4:** South Dakota, Arkansas, Minnesota, Wisconsin, North Dakota, Illinois, Missouri, Iowa, Texas, Oklahoma, Kansas, Nebraska, Wyoming, Colorado;
- **Analysis Center 5:** Utah, New Mexico, Arizona, California, Oregon, Washington, Idaho, Hawaii, Alaska, Montana, Nevada
- **Analysis Center 6:** ROW – sites in Australia and the Netherlands

## 5.8 Multiple Comparisons/Multiplicity Adjustment

A hierarchical procedure will be used to control the overall Type I error rate at 0.05 for the primary endpoint and the secondary endpoints across the 2 AK002 dose regimens vs. placebo. Each hypothesis will be formally tested only if the preceding hypothesis is significant at the 2-sided 0.05 significance level. The hierarchical testing order (all comparisons are with the placebo) is as follow:

**Table 7 Hypothesis Testing Order Hierarchy**

Endpoint Description	AK002 IV Dose Groups	
	Low Dose	High Dose
Primary Endpoints		
1) The proportion of subjects who achieve a peak esophageal intraepithelial count of $\leq 6$ eosinophils/hpf at Week 24.	8	1
2) Mean change in DSQ score from Baseline to Weeks 23–24.		
Secondary Endpoints		
1) Percent change in peak esophageal intraepithelial eosinophil count at Week 24.	14	7
2) Proportion of subjects achieving peak esophageal intraepithelial eosinophil count of $\leq 1$ eosinophil/hpf at Week 24.	9	2
3) Proportion of subjects achieving peak esophageal intraepithelial eosinophil count of $< 15$ eosinophils/hpf at Week 24.	18	17
4) Proportion of treatment responders when a responder is a subject achieving $> 30\%$ reduction in symptoms (DSQ) at Weeks 23–24 and achieving a peak intraepithelial eosinophilic count of $\leq 6$ eosinophils/hpf at Week 24.	10	3
5) Proportion of subjects with $> 50\%$ reduction in DSQ score from Baseline to Weeks 23–24.	12	5
6) Percent change in DSQ score from Baseline to Weeks 23–24.	11	4
7) Change in biweekly mean DSQ over time.	16	15
8) Change in EoE Endoscopic Reference Score from Baseline to Week 24.	13	6

## 5.9 Examination of Subgroups

Key endpoints will be summarized by subgroup to assess the consistency of the treatment effect across subgroups. Subgroups to be considered are:

- Gender (Male, Female)
- Age (12–17,  $\geq 18$ )
- Race (White, Non-White)
- Baseline DSQ ( $\leq 30$ ,  $> 30$ )

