### 3.6 Determination of Sample Size

To achieve statistical significance for the first co-primary endpoint, a sample size of 8 subjects per treatment group will provide 90% power to demonstrate a statistically significant difference between AK002 and placebo in achieving the histological response (defined as the peak esophageal intraepithelial eosinophil count  $\leq 6$  cells/hpf) at Week 24. This calculation is based on the AK002-003 study in which 90% of AK002 subjects and 10% of placebo subjects achieved the histologic response at Day 99. The hypothesized treatment effect of 80% yielded a small number of subjects per group for the first co-primary endpoint.

To achieve statistical significance for the second co-primary endpoint, a sample size of 86 subjects per treatment group will provide 90% power to demonstrate a statistically significant difference between any AK002 dose group and placebo treatment group in mean absolute change in DSQ score from baseline to Weeks 23–24. This calculation is based on the baseline score of  $30 \pm 15$  (mean  $\pm$  Standard Deviation [SD]) reported in the literature, and an expected mean reduction of 15 in the AK002 group and 7.5 in the placebo group, and a SD of 15 for the change from baseline (Dellon, 2021; Hirano, 2019; Hudgens, 2017).

Consequently, approximately 100 subjects per treatment group will be included for a total of 300 subjects, driven by the second co-primary endpoint and a potential 14% dropout rate.

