### 6.11.3 Subgroup Analysis of the First Co-Primary Endpoint

Analysis comparing AK002 and placebo will use Fisher’s exact test for each of the subgroups defined in Section 5.9.

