#### **6.11.6 Supplementary Analyses**

Analysis described in Section 6.11.2 will be repeated for the PP population.

Additional analysis will investigate the treatment effect on DSQ change from baseline in the subgroups defined in Section 5.9. This analysis will use ANCOVA similarly to the primary analysis (Section 6.11.2).

Empirical cumulative distribution function (eCDF) of the change from baseline in DSQ will be plotted by treatment group to demonstrate consistency of the treatment effect.

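### The subgroup plan aims at consistency of the treatment effect, but it only estimates and tests the effect inside each subgroup and never compares it between subgroup levels

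*SAP*

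**What the plan says.** SAP 5.9 states the purpose: "Key endpoints will be summarized by subgroup to assess the consistency of the treatment effect across subgroups". It lists four two-level factors: gender, age (12–17, 18 and over), race (White, Non-White) and baseline DSQ (cut at 30).

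For histology, SAP 6.11.3 compares AK002 with placebo by Fisher's "exact test for each of the subgroups defined in Section 5.9". For DSQ, SAP 6.11.6 says: "Additional analysis will investigate the treatment effect on DSQ change from baseline in the subgroups defined in Section 5.9", using an ANCOVA modelled on the primary analysis. That analysis, in SAP 6.11.4, gives least squares means, standard errors and 95% CIs for each group and for the between-group difference, and tests the treatment effect with an F-test.

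The only treatment interactions in either document are with week or visit, in the repeated-measures models (Protocol 15.7; SAP 6.12.6 and 6.13). The output list in SAP Appendix 3 has one subgroup table per factor for each co-primary endpoint. Its two figures are a cumulative distribution plot and a tipping-point plot, so no forest plot is listed.

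SAP 6.11.6 refers to 6.11.2 for the primary ANCOVA. Section 6.11.2 is the stratified sensitivity analysis of histology; the ANCOVA is in 6.11.4.

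**The concern.** Consistency is a question about two effects at once: is the AK002–placebo difference the same in both levels of a factor? A test inside one level asks whether the effect there is zero, and its result depends heavily on how many subjects that level contains. The two questions have different nulls, and the plan supplies a test only for the second.

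The trial enrols adolescents and adults together and stratifies randomisation by age and baseline DSQ (Protocol 10.2). Whether the symptom benefit extends to ages 12–17, or to both severity groups, is therefore something the report will be asked. As planned, the tables would not contain the quantity that answers it, and nothing in the SAP guards against reading a significant result in one level and a non-significant result in the other as a difference in effect.

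**Working it through.** **Inputs.** From SAP 3.6: "an expected mean reduction of 15 in the AK002 group and 7.5 in the placebo group", so an effect of 15 − 7.5 = 7.5 points; "a SD of 15 for the change from baseline"; about 100 randomised per arm. From SAP 5.8: tests are "significant at the 2-sided 0.05 significance level". Subgroup shares are not given, so a range is assumed. Each calculation is one dose against placebo, by unadjusted two-sample t-test (noncentral t).

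**Reproducing the plan's figure.** SAP 3.6 says "a sample size of 86 subjects per treatment group will provide 90% power to demonstrate" a difference. With n = 86 per arm the noncentrality is 7.5 / (15 × √(2/86)) = 3.28 and power is 90.3%, which agrees. Allowing for dropout, 86 / 0.86 = 100 per arm; power with all 100 is 94.0%.

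**Reading by significance.** Let a and b be the powers in the two levels when the true effect is 7.5 in both. The levels contain different subjects, so:

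- both significant = a × b
- discordant (one significant, one not) = a(1 − b) + b(1 − a)

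For the last column the effect in the smaller level is truly zero, so a = 0.05.

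| Smaller level (assumed) | n per arm, small / large | Power, small / large | Both significant | Discordant, same effect | Discordant, no effect in smaller level |
|---|---|---|---|---|---|
| 5% | 5 / 95 | 11% / 93% | 10% | 84% | 89% |
| 10% | 10 / 90 | 19% / 92% | 17% | 76% | 87% |
| 20% | 20 / 80 | 34% / 88% | 30% | 62% | 84% |
| 50% | 50 / 50 | 70% / 70% | 49% | 42% | 68% |

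Example at 10%: 0.185 × 0.084 + 0.916 × 0.815 = 0.762 with the same effect in both levels, and 0.05 × 0.084 + 0.916 × 0.95 = 0.874 with none in the smaller level. The pattern is nearly as common when the effect is consistent as when it is not, so it separates the two cases poorly. With 86 evaluable per arm, discordance under the same effect is 47% at an even split and 74% at 10%.

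**The one share that can be approximated.** SAP 3.6 assumes baseline DSQ of 30 ± 15 and the cut is 30, so a normal distribution gives an even split. Truncating at the entry minimum of 12 (Protocol 7.3) gives (0.500 − 0.115) / 0.885 = 43% at or below 30. Discordance for this factor is then 42–43% with 100 per arm and 47–48% with 86.

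**Sensitivity to covariate adjustment.** If ANCOVA lowers the residual SD to about 13 (assumed correlation 0.5: 15 × √0.75 = 13.0), discordance at an even split with 100 per arm falls to 30%.

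**Comparing the effects directly.** The standard error of the difference between two subgroup effects is 15 × √(2/n₁ + 2/n₂): 4.24 points at 50/50 and 7.07 at 10/90. The 95% CI is roughly ±8.3 and ±13.9 points (1.96 × SE). A 5% interaction test flags a consistent effect in 5% of trials per factor. Its power against 7.5 versus 0 is only about 12% / 18% / 29% / 42% at shares of 5 / 10 / 20 / 50%.

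**Histology.** At the planning rates of 90% versus 10%, exact enumeration gives Fisher's test 74% / 93% / 96% power at 5 / 8 / 10 per arm. The size-dependence bites only in very small subgroups or at lower response rates (60% versus 10%: 47% at 10 per arm).

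**The case against.** The strongest reply is that the discordance figures need a decision rule the SAP does not contain. Section 5.9 speaks of summarising, 6.11.6 places the DSQ subgroups among supplementary analyses, and none of these tests is in the Table 7 hierarchy. The DSQ analysis also inherits from 6.11.4 the within-subgroup differences with standard errors and 95% CIs. Because the two levels hold different subjects, a reader could subtract the differences and obtain an approximate standard error as the root of the summed squares. All of this stands. It makes the matter one of reporting and interpretation. What remains is that no comparison between levels is specified and no basis for judging consistency is stated, although 5.9 names consistency as the purpose.

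A reader might go further and infer that a fully consistent DSQ effect would usually look inconsistent under this plan, or that a null result in adolescents or Non-White subjects is the expected outcome. The documents do not support that. They set no p-value rule and give no share for either group. The one share that can be approximated, baseline DSQ, gives discordance below one half. Higher figures need small assumed minority shares, or a count of any discordance among the four factors.

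It is also fair to say that an interaction test is weak here. That is a reason to rely on the estimate and its CI, and not on the p-value.

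**Conclusion.** The concern holds in limited form. The plan sets out to assess consistency across subgroups but contains only within-subgroup estimates and tests, with nothing that compares the effect between levels. Co-primary and secondary conclusions are untouched, and histology is little affected at the planning rates.

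For DSQ, if consistency were read from within-subgroup significance, an identical 7.5-point effect would appear discordant for a given factor in about 42% of trials at an even split and in 62–84% with a smaller level of 20% down to 5%. This rests on the SAP's effect and SD, 100 per arm, an unadjusted comparison and assumed shares; covariate adjustment would lower the even-split figure. The change is worth making because it is cheap and supplies the quantity that 5.9 asks for.

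**What to change.** **DSQ (SAP 6.11.6).** For each 5.9 factor and each dose against placebo, fit one ANCOVA to the MITT population with treatment, subgroup, treatment-by-subgroup, baseline DSQ and age strata, combined over the imputed data sets as in 5.4.2. When age is the subgroup, enter it only once. Report the difference between the two subgroup effects with its 95% CI, and treat the interaction p-value as descriptive. Show within-subgroup effects as estimates with CIs.

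**Imputation.** The model described in 5.4.2 uses baseline eosinophil count, baseline DSQ, age strata and the biweekly scores. Add gender and race to the version used for these subgroup analyses; without them, imputed values would tend to pull the gender and race interactions towards zero.

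**Histology (SAP 6.11.3).** Within-subgroup risk differences with 95% CIs are enough.

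**Wording.** State in 5.9 that consistency is judged from these estimates and intervals, not from within-subgroup significance. Correct the cross-reference in 6.11.6 from 6.11.2 to 6.11.4.

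**Cost.** SAP text, a few model terms, an additional imputation run and extra rows in Tables 14.2.2.5.1 to 14.2.2.5.4 (and CIs in 14.2.1.2.1 to 14.2.1.2.4). No new data or subjects are needed. The drawback is low power for the interaction, about 12–42% against 7.5 versus 0, so its interval will be wide. That width reflects how little a trial of this size can say about differences between subgroups.

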## **6. Statistical Analysis**

### **6.1 Analysis Populations**

The population of “all screened subjects” comprises subjects who signed the informed consent form (ICF).

#### **6.1.1 Safety Population**

The safety population comprises randomized subjects who have received at least 1 dose of the study drug.

#### **6.1.2 Intent-to-Treat Population**

The Intent-to-Treat (ITT) population is defined as subjects who were randomized to treatment.

#### **6.1.3 Modified Intent-to-Treat Population**

The Modified Intent-to-Treat (MITT) population is defined as subjects who were randomized and received at least 1 dose of study drug.

#### **6.1.4 Per Protocol Analysis population**

The Per Protocol (PP) population will include the MITT population who have received at least 1 dose of study drug and did not have major protocol violations potentially interfering with the efficacy assessment. The PP exclusion criteria will be specified prior to the database lock and unblinding.

#### **6.1.5 Primary Analysis population**

The MITT population is the primary analysis population for all efficacy and safety analyses. Analysis using the ITT population will be carried out if  $\geq 5$  randomized subjects do not receive study drug. The PP population will be used to evaluate robustness for the primary endpoints and select secondary endpoints when appropriate.

### **6.2 Disposition of Subjects**

Subject demographics and reasons for screening failure will be summarized for screen-failed subjects.

Subjects (n and %) who completed or discontinued from the study will be tabulated by treatment group and for both treatment groups combined. The primary reasons for study discontinuation will be included in the tabulation. The primary reasons may include, but are not limited to, any of the following:

- Subject withdrew consent
- Lost to follow-up
- Administrative reason
- Adverse event
- Investigator decision
- Failure to follow required study procedures
- Other

Subject disposition will be summarized for all enrolled subjects. Subject counts for the Safety, MITT, and PP populations will be included in the table. A data listing for subject disposition will be presented for all enrolled subjects.

### **6.3 Protocol Deviations**

Protocol deviations will include, but are not limited to:

- Non-compliance with scheduled study visit
- Non-compliance with study treatment
- Received prohibited medications (see Protocol Section 8.1)
- Non-compliance with study inclusion or exclusion criteria
- Non-compliance with study assessment procedures

Subjects with major protocol deviations will be listed. The listing will include a brief description of the deviation, deviation category, and if applicable, study day when deviation occurred along with other pertinent information.

If warranted by the sample size, subjects (n and %) with major protocol deviations will be tabulated by treatment group and by deviation category.

Subjects who are excluded from the PP population will be listed with reasons for exclusion.

### **6.4 Demographics and Baseline Subject Characteristics**

Descriptive statistics for subject characteristics and baseline values will be presented for all populations by treatment group and both treatment groups combined. Continuous variables will be summarized with n, mean, SD, and median. Categorical variables will be summarized with n and % of subjects for each category for the MITT and PP populations.

## **6.5 Baseline Disease Characteristics**

Baseline disease characteristics including demographics, baseline DSQ score, and medical history will be included in the subject data listing.

## **6.6 Medical History**

Subject incidence (n and %) of medical history (and current medical condition before signing the ICF will be tabulated by the Medical Dictionary for Regulatory Activities (MedDRA) (version 21.0) System Organ Class (SOC) and Preferred Term (PT).

## **6.7 Electrocardiogram**

A listing of ECG overall interpretation at screening visit will be provided.

## **6.8 Pregnancy Test**

A listing of pregnancy test results will be provided.

## **6.9 Baseline Diet**

A listing of baseline and on-study diet assessment and compliance will be provided.

## **6.10 Treatments**

### **6.10.1 Treatment Compliance and Extent of Exposure**

Summaries of treatment compliance and exposure to AK002 will be based on the safety population.

Duration of treatment exposure is defined as the total number of days a subject is exposed to the study treatment. This will be calculated for each subject by taking the difference between the date of the last dose minus the date of the first dose, plus 1 (date of last dose – date of first dose +1).

Duration of exposure will be summarized using descriptive statistics (n, mean, SD, median, minimum, and maximum).

Treatment compliance is defined as the number of infusions subjects received divided by 6 (i.e., total number of infusions expected)  $\times$  100%. Treatment compliance will be summarized descriptively. In addition, overall compliance that includes adherence to the treatment administration schedule and any interruptions will be included in the data listing.

The treatment infusion information (length, volume, rate, and interruption) will be included in the subject data listing.

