2.3 Overview of Clinical Studies

AK002, administered as a monthly intravenous infusion, has previously been tested in healthy volunteers and in subjects with indolent systemic mastocytosis (ISM), chronic urticaria, severe allergic conjunctivitis (AC), mast cell gastritis, and eosinophilic gastritis (EG) and/or eosinophilic duodenitis (EoD), referred to as eosinophilic gastroenteritis (EGE) in previous studies.

Multiple doses of 3 mg/kg have been given to subjects with ISM, chronic urticaria, severe AC, mast cell gastritis, and EG and/or EoD. In these studies, AK002 pharmacodynamic (PD) activity was observed for prolonged periods of time and the AK002 pharmacokinetic (PK) parameters demonstrated a half-life amenable to administration every 4 weeks.

To date, 51 healthy volunteers (36 on AK002, 15 on placebo), 25 subjects with ISM, 47 subjects with chronic urticaria (including spontaneous and inducible), 30 subjects with severe AC, 8 subjects with mast cell gastritis, and 65 subjects with EG and/or EoD (43 on AK002 and 22 on placebo) have been enrolled in clinical studies.

In general, AK002 was well tolerated. The most common treatment-emergent adverse event (TEAE) observed was infusion-related reactions (IRR). Most IRR were mild to moderate and 2 IRR (1 in the healthy volunteer study and 1 in the AK002-003 study) were serious but resolved within 24 hours. Common symptoms of IRR were headache, nausea, sweating, flushing, and redness. Most IRR occurring during the infusion could be managed by slowing or temporary interruption of the infusion, with minimal intervention. In 6 healthy volunteers who received 2 doses of 0.3 mg/kg, 4 weeks apart, the second dose was better tolerated than the first dose. This is also the case in patients with ISM, chronic urticaria, severe AC, and EG and/or EoD; fewer adverse events (AE) were reported during the second and subsequent infusions when compared to the first infusion.

In all studies, a transient decrease in lymphocyte counts was observed after the AK002 infusion (usually resolving within 1 day) that was not associated with any clinical consequence, and a sustained depletion of eosinophils was observed that is consistent with the mechanism of action of AK002. No significant trends were observed for changes in vital signs, electrocardiograms (ECG), clinical laboratory parameters, or physical examinations.

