9.6 Study Drug Administration

Specific instructions on administration and supplies required for administration are detailed in the Pharmacy Manual. In general, study drug will be infused through a peripheral vein IV set. The IV line will be kept open before and after the infusion with sufficient quantities of 0.9% NaCl to assure patency.

A volume of 100 mL* of placebo or AK002 at a dose of 1 mg/kg will be prepared according to the subject's body weight and administered over ≥ 4 hours on Day 1. Subsequent infusions of placebo or AK002 at a dose of 1 mg/kg or 3 mg/kg will be prepared on Day 29 (± 3), Day 57 (± 3), Day 85 (± 3), Day 113 (± 3), and Day 141 (± 3). Depending on the subject's tolerance of the first and subsequent infusions (and at the Investigator's discretion), the second infusion can be given over ≥ 3 hours, and the subsequent 4 infusions can be given over ≥ 2 hours. If the infusion is slowed or interrupted, the infusion length may exceed 4 hours but must be completed within 8 hours of preparation (prior to expiry). The same applies to the first and subsequent infusions in the OLE period of the study (for eligible subjects that choose to participate in the OLE period).

* Due to rounding of the total infusion volume by some programmable infusion pumps, an infusion of 99 mL to 101 mL will be considered a complete infusion and will not be recorded as a deviation from the study.

Prior to the first dose of study drug (12–24 hours prior to the infusion), subjects will be premedicated with oral prednisone (40 mg if body weight is <40 kg, 60 mg if body weight is ≥ 40 kg and <60 kg, or 80 mg if body weight is ≥ 60 kg). Subjects will self-administer oral prednisone 12–24 hours prior to the start of the first infusion only. As treatment assignment during the double-blind, placebo-controlled part of the study will be blinded, all eligible subjects that choose to participate in the OLE period of the study will self-administer oral prednisone premedication 12–24 hours prior to the first OLE period infusion as well.

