### 3. Study Design

#### 3.1 General Description

This is a Phase 2/3, multicenter, randomized, double-blind, placebo-controlled study to evaluate the safety, tolerability, and clinical benefit of AK002 in adult and adolescent subjects with active EoE. Subjects enrolled in the study will receive 6 infusions of placebo or AK002 administered every 4 weeks and will be followed for 8 weeks after the last dose.

Subjects who complete the double-blind, placebo-controlled treatment and the Day 169 visit may have the option to receive 6 doses of open-label AK002 through participation in the optional Open-Label Extension (OLE) Period of the study and will be followed for 8 weeks after the last dose.

Subjects will be consented and then screened for 14 to 60 days. During the screening period, a baseline, stable regimen of proton pump inhibitors (PPI) and/or dietary intake will be established, if needed, and baseline disease activity data will be collected. Swallowed topical corticosteroids and systemic corticosteroids will not be allowed. Subjects who meet eligibility criteria can be enrolled in the study. Subjects who do not meet all eligibility criteria at screening, or who qualify at screening but are not enrolled, may be assigned a new subject identification number and rescreened once. Subjects rescreened within 30 days of signing the initial informed consent form (ICF) will not need to re-consent if no changes have been made to the ICF.

Prior to the first dose of study drug (12–24 hours prior to the infusion), subjects will be premedicated with oral prednisone (40 mg if body weight is <40 kg, 60 mg if body weight is ≥40 kg and <60 kg, or 80 mg if body weight is ≥60 kg). Subjects will self-administer oral prednisone 12–24 hours prior to the start of the first infusion only.

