#### 3.3.2 Duration of Study

The total study duration for each subject will be either 33–36 weeks or 58–61 weeks, including and depending on:

- Screening Period of 14–60 days (or a maximum of 35 days after the Screening EGD, whichever is shorter) prior to study drug administration.
- Treatment Period of 24 weeks ( $\pm 3$  days) beginning the day of the first dose and ending 4 weeks after the last dose
- Optional Open-Label Extended Dosing Period of 28 weeks ( $\pm 3$  days), or Follow-up period of 4 weeks ( $\pm 3$  days).

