#### **4.2.3 Treatment**

AK002 or placebo administered to subjects on Days 1, 29, 57, 85, 113, and 141.

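### The duration-of-exposure formula in SAP 6.10.1 stops on the day of the last infusion and leaves out the final 4-week dosing interval, so a full course reads 141 days instead of 168

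*SAP*

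**What the plan says.** SAP 6.10.1 first states what is to be measured: "Duration of treatment exposure is defined as the total number of days a subject is exposed to the study treatment". It then gives the derivation as "taking the difference between the date of the last dose minus the date of the first dose, plus 1", and summarizes the result with n, mean, SD, median, minimum and maximum. The output is SAP Table 14.1.7.3, on the Safety population.

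The dosing schedule is in SAP 4.2.3: "AK002 or placebo administered to subjects on Days 1, 29, 57, 85, 113, and 141". SAP 3.1 gives the same spacing: "Subjects enrolled in the study will receive 6 infusions of placebo or AK002 administered every 4 weeks". SAP 3.3.2 sets the treatment period at 24 weeks, "beginning the day of the first dose and ending 4 weeks after the last dose".

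Protocol 2.3 supports the interval from earlier studies, where the pharmacokinetic "parameters demonstrated a half-life amenable to administration every 4 weeks". Protocol 15.6 does not define a duration. It plans only a count of subjects by the number of infusions received.

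**The concern.** Last date minus first date plus 1 gives days on treatment when a product is taken daily, because exposure then ends roughly with the last dose. Here one infusion is meant to cover 4 weeks. The formula credits that interval to every infusion except the last, to which it credits 1 day. The stated quantity and its derivation therefore disagree within the same paragraph of the SAP, and the derivation also disagrees with the treatment period in SAP 3.3.2.

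The exposure summary is where a reader looks to see how much treatment experience supports the safety tables. A subject who stops after one infusion would appear there with 1 day of exposure. Yet the early termination visit for that subject is planned 28 days after the dose (note 32 to the Schedule of Events), and adverse events are collected until then. Anyone who set event counts against the table would be using too small a denominator.

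**Working it through.** **Inputs.** Dosing days 1, 29, 57, 85, 113 and 141 (SAP 4.2.3), spaced 28 days apart. Treatment period of 24 weeks from first dose to 4 weeks after the last (SAP 3.3.2). Exposure formula from SAP 6.10.1.

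**Step 1: reproduce the plan's treatment period.** First to last dose is 141 − 1 = 140 days. Adding 28 gives 168 days, and 168 / 7 = 24 weeks. This matches SAP 3.3.2.

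**Step 2: apply the two formulas.** SAP: last − first + 1. With the final interval included, and the dosing day counted as day 1 of its interval: last − first + 28.

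| Infusions received | Day of last infusion | SAP formula (days) | With final interval (days) | Shortfall (days) | Shortfall (%) |
|---|---|---|---|---|---|
| 1 | 1 | 1 | 28 | 27 | 96.4 |
| 2 | 29 | 29 | 56 | 27 | 48.2 |
| 3 | 57 | 57 | 84 | 27 | 32.1 |
| 4 | 85 | 85 | 112 | 27 | 24.1 |
| 5 | 113 | 113 | 140 | 27 | 19.3 |
| 6 | 141 | 141 | 168 | 27 | 16.1 |

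The six-dose value in the fourth column equals the plan's own 24 weeks; the SAP formula gives 141 / 7 = 20.1 weeks.

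**Step 3: visit windows.** The difference between the formulas is 28 − 1 = 27 whatever the dates. A sixth infusion 7 days early gives 134 against 161; 7 days late gives 148 against 175.

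**Step 4: truncation.** If follow-up ends t days after the last dose, only those t days can be missing, so the shortfall is the smaller of t and 27: 7 days if t = 7, 14 if t = 14, and 27 from t = 27 onward. For open-label dosing the interval after an on-schedule sixth infusion ends on Day 168, and after one given 3 days late on Day 171. The first open-label dose is planned for Day 176 ± 3, so Day 173 at the earliest. The cap therefore matters only when visits use the wider ± 7-day tolerance.

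**Step 5: counting convention.** If the day exactly 28 days after the last dose (Day 169) is also counted, a full course is 169 days and the shortfall is 28.

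**The case against.** The strongest reply is that first-to-last-dose duration is unambiguous and reproducible, and is simply a choice of definition. SAP 3.3.2 defines a study period, not exposure. Adding 28 is itself a convention: Protocol exclusion criterion 15 equates five half-lives with up to 4 months, or roughly 120 / 5 = 24 days each, so drug remains in the body beyond 28 days after a dose. All of that is fair as far as it goes. But the SAP does not present its figure as dosing duration. It presents it as days exposed, and on that reading stopping at the last infusion is the one choice that its own schedule rules out. The half-life argument points to longer exposure, not shorter.

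The reply is also right that little depends on the number. Adverse events are summarized as numbers and percentages of subjects, with no exposure-adjusted rate. Protocol 15.6 counts infusions, so a one-dose subject remains identifiable.

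Four stronger readings are tempting, and the documents do not support them.

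- A reader might infer that every subject is 27 days short, or 27 × 100 = 2,700 subject-days per arm of 100. Those are ceilings, because truncation lowers the figure for some subjects.
- A reader might infer that the error is largest for early stoppers. That holds in percentage terms only; in days it is never larger for them.
- A reader might infer that the correction would align exposure with the period in which adverse events are counted. It would not: subjects outside the open-label period are followed for events to Day 197.
- A reader might infer that compliance is inflated too, since "Treatment compliance is defined as the number of infusions subjects received divided by 6" while Protocol 9.6 says "an infusion of 99 mL to 101 mL will be considered a complete infusion". SAP 6.10.1 does not say that a partial infusion counts as one received, and it lists infusion volume and interruptions by subject. The 99–101 mL range is a note about pump rounding, not an analysis threshold.

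**Conclusion.** The point holds as an error of definition with low impact. Followed as written, SAP 6.10.1 understates duration of exposure by up to 27 days per subject: 16% for a completed on-schedule course and 96% for a single infusion. This rests on crediting each infusion with the 28-day interval at which the plan doses, with the dosing day as day 1, which is the convention that reproduces the SAP's 168-day treatment period.

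The consequence is limited to the descriptive duration lines of Table 14.1.7.3. No hypothesis test, efficacy estimate or event rate depends on them. The offset is the same in all arms apart from differences in truncation, so comparisons of mean duration between arms are essentially unaffected. What is wrong is the absolute level of exposure, and its relative level in subjects who stop early.

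**What to change.** In SAP 6.10.1, replace the derivation with last dose date − first dose date + 28, truncated at the earliest of death, study exit and the day before the first open-label dose. State that the dosing day counts as day 1 of its interval. If the sponsor prefers to keep the present figure, report it alongside under the label first-to-last infusion, so that it is not read as days exposed.

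The cost is one derivation line plus a truncation rule and a table label. All the dates needed are already collected, and no other planned output changes.
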